## ② Use of other drugs

Presence/absence of concomitant drug use for conditions other than JIA, names of drugs, routes, doses, and durations

If an adverse event occurs: Names of drugs, reasons for use, routes, doses, and durations

- 6) Non-drug concomitant therapy
  - Non-drug concomitant therapy for JIA
- 7) Presence/absence of tuberculosis or serious respiratory diseases
  - Date of confirmation, method of diagnostic imaging, and presence/absence and type of abnormal findings
- 8) Clinical evaluation
  - Patients will be evaluated for the following at the time points described below:
    - ① DAS28 (number of tender joints and number of swollen joints), global assessment by patient (VAS), global health by physician (VAS), erythrocyte sedimentation rate (ESR, 1 hr value), and CRP. (Baseline, and Weeks 4, 8, 16, and 24 weeks of treatment)
    - ② Serum MMP-3 level. (Baseline, and Weeks 4, 8, 16, and 24 weeks of treatment)
    - ③ Anti-CCP antibody (Baseline and 24 weeks of treatment)
    - ④ Height and body weight. (Baseline, and Weeks 4, 8, 16, and 24 weeks of treatment)
- 9) Discontinuation of Humira treatment
  - Reasons for discontinuation of Humira treatment
  - Treatment after discontinuation of Humira treatment
- 10) Adverse events (including abnormal laboratory findings)
  - Presence/absence of adverse events, nature of adverse events, dates of onset, seriousness, causal relationship with Humira treatment, suspected drugs, clinical course of adverse events, measures taken (measures related to Humira treatment and symptomatic treatment), outcomes, and laboratory findings (indicate laboratory values when abnormal laboratory findings are observed).
- 11) Items of investigation of particular interest
  - Occurrence of infections, tuberculosis, malignant tumor, administration site reactions, autoimmune diseases, pancytopenia, demyelinating disease, congestive heart failure, and interstitial pneumonia.

(4) Preparation of written consent form for transition to self-injection and self-injection transition record

It will be confirmed whether written consent for transition to self-injection has been obtained and a self-injection transition record has been prepared.

(5) Presence/absence of malignant tumor during the long-term follow-up period.

Patients will be evaluated for the occurrence of malignancy during the first and second years of treatment.

(6) Product Quality Complaints

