Patients excluded from the efficacy analysis set	
Of the patients included in the safety analysis set, those who meet any of the following from the list of inclusion of patients.
 
 
Disease not eligible to the survey
 
Disease defined as not eligible to the survey in the implementation plan
 
Patient ineligible for efficacy assessment
 
DAS 28 (4/ESR) cannot be calculated at any time points after administration of Humira
 

Patients included in the efficacy analysis set	Patients included in the safety analysis set excluding patients excluded from the efficacy analysis set.

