## 9. General agreements concerning analysis

### 9.1. Handling of missing data

Missing data will not be complemented, etc. during analysis. However, input data need to be complemented for some items. For the input data requiring complement, the complement methods are defined in the definition of each item in Chapter 10 and subsequent chapters.

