### 9.3. Handling of unknown/unspecified

For calculation of percentage, the number of patients with “unknown” or “unspecified” data should be included in denominators. When a test is performed, patients with “unknown” or “undescribed” data should be excluded.

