Footnotes	
Where it is considered necessary to provide an explanation in association with preparation of analysis results, provide the explanation in a footnote.
 
Footnotes should be in the following form:
 
Add a superscript “*sequential number” on the right side of a term, etc. that you want to explain, and provide the “*sequential number” corresponding to the footnote and the explanation under the diagram.

Percentage	
When a percentage is calculated, the denominator should be the number of patients in the analysis set.
 
*Specify in a footnote when the denominator used for calculation of a percentage in the same table is different from the number of patients in the analysis set.
 
When percentages for a breakdown of a factor or item are calculated, ensure that the total becomes 100%. Any item redundantly counted should be specified in a footnote.

Context of numbers	When a figure such as a patient composition figure is created, all numbers required to maintain consistency of the context of numbers should be provided.

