## 11. Data-layer separation

Data	Layer separation
Reason for discontinuation	Remission, subtherapeutic response, onset of adverse events, patient's request, no hospital visit (including hospital transfer), other
Reason for switching	Remission, subtherapeutic response, onset of adverse events, patient's request, no hospital visit (including hospital transfer), other
Sex	Male, female, unknown/unspecified
Pregnancy/breastfeeding	Not pregnant/breastfeeding, pregnant, breastfeeding, unknown/unspecified
Age 1	$\leq 6$ years, $>6$ years
Age 2	$<15$ years, $\geq 15$ years and $<65$ years, $\geq 65$ years
Age 3	$<6$ years, $\geq 6$ years and $<11$ , $\geq 11$ years and $<16$ years, $\geq 16$ years and $<21$ years, $\geq 21$ years
Body weight	$<15$ kg, $\geq 15$ kg and $<30$ kg, $\geq 30$ kg, unknown/unspecified
BMI( $\text{kg}/\text{m}^2$ )	$<18.5$ $\text{kg}/\text{m}^2$ , $\geq 18.5$ $\text{kg}/\text{m}^2$ and $<25.0$ $\text{kg}/\text{m}^2$ , $\geq 25.0$ $\text{kg}/\text{m}^2$ and $<30.0$ $\text{kg}/\text{m}^2$ , $\geq 30.0$ $\text{kg}/\text{m}^2$ and $<35.0$ $\text{kg}/\text{m}^2$ , $\geq 35.0$ $\text{kg}/\text{m}^2$ , unknown
Inpatient/outpatient status at the start of Humira treatment	Inpatient, outpatient, unknown/unspecified
Reason for use and type of disease	Generalised arthritis, oligoarthritis (persistent), oligoarthritis (extended), polyarthritis (RF negative), polyarthritis (RF positive), other, unknown/unspecified
Disease duration 1	$<6$ months, $\geq 6$ months and $<1$ year, $\geq 1$ year and $<2$ years, $\geq 2$ years and $<3$ years, $\geq 3$ years and $<5$ years, $\geq 5$ years and $<10$ years, $\geq 10$ years and $<20$ years, $\geq 20$ years, unknown/unspecified
Disease duration 2	$<5$ years, $\geq 5$ years, unknown/unspecified
Race	Japanese, other, unknown/unspecified
Steinbrocker Staging System	Stage I, Stage II, Stage III, Stage IV, unknown/unspecified
Steinbrocker Functional Classification	Class I, Class II, Class III, Class IV, unknown/unspecified
Administration method category	Self-administration, self-administration $\leftrightarrow$ administration by a doctor, administration by a doctor, unknown/unspecified
Past medical history	No, yes, unknown/unspecified
Complications	No, yes, unknown/unspecified
Breakdown of complications	Liver disorder, renal disorder, cardiovascular disorder, blood disorder, respiratory disorder, other
Complication: Liver disorder	No, yes, unknown/unspecified
Complication: Renal	No, yes, unknown/unspecified

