## 12. Handling of data on tests/timing of assessment

Timing and period category	Handling of data
Time window for efficacy assessment	Before the start of treatment: from the start date of Humira treatment - 30 days to the start date of Humira treatment At Week 4 of treatment: from the start date of Humira treatment + 1 day to the start date of Humira treatment + 42 days At Week 8 of treatment: from the start date of Humira treatment + 43

Timing and period category	Handling of data
	
days to the start date of Humira treatment + 70 days
 
At Week 12 of treatment: from the start date of Humira treatment + 71 days to the start date of Humira treatment + 98 days
 
At Week 16 of treatment: from the start date of Humira treatment + 99 days to the start date of Humira treatment + 140 days
 
At Week 24 of treatment: from the start date of Humira treatment + 141 days to the start date of Humira treatment + 196 days
 
At the final assessment: the data measured at the end during the period from the start date of Humira treatment + 1 day to the start date of Humira treatment + 196 days.

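### Patients never scored on DAS28-4/ESR after starting Humira leave the efficacy set even if the CRF records stopping for lack of effect or an adverse event, so remission and EULAR rates may be inflated

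*SAP*

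**What the plan says.** SAP section 8 defines the efficacy set as "Patients included in the safety analysis set excluding patients excluded from the efficacy analysis set". Apart from an ineligible disease, the ground for exclusion is that "DAS 28 (4/ESR) cannot be calculated at any time points after administration of Humira". The reason why treatment stopped plays no part in this rule.

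Three other SAP rules decide what happens to an excluded patient:

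- Section 9.1: "Missing data will not be complemented, etc. during analysis". Chapter 10 defines no replacement value for DAS28.
- Section 9.10: "When a percentage is calculated, the denominator should be the number of patients in the analysis set". A patient outside the set is therefore in neither numerator nor denominator.
- Section 10.3 defines remission and EULAR response by DAS28 values alone. Neither definition has a category for a patient who stopped treatment and was never scored.

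The protocol (section 8, Clinical evaluation) schedules DAS28 at "Baseline, and Weeks 4, 8, 16, and 24 weeks of treatment". SAP section 11 classifies the reason for discontinuation as "Remission, subtherapeutic response, onset of adverse events, patient's request, no hospital visit (including hospital transfer), other". Under SAP section 10.1, the adverse-event reason counts only if an adverse event in the safety analysis period is also on record.

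Tables 3.1, 3.5.1, 3.5.2 and 3.5.3 all use the efficacy set or its DAS28-4/ESR version. No efficacy table uses a wider set.

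**The concern.** The first scheduled score after the start is at Week 4. A patient who gives up treatment before then may never be scored. If the recorded reason is lack of effect, the data already show how treatment went, yet the plan handles that patient exactly like one whose ESR was simply not measured.

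The survey enrols all treated patients in order to describe use in practice, and factors affecting efficacy are one of its stated purposes. If unscored failures drop out, the remission and EULAR rates describe those who stayed long enough to be scored. Tables 3.1 and 3.5.2 also test about 30 background factors on this set. A factor that goes with early failure would lose those failures from its own test.

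**Working it through.** **The plan's own figure.** The only design figure is in protocol section 2: 100 patients to detect an adverse reaction of 3% incidence with 95% probability. 1 − 0.97^100 = 0.952, so it is reproduced. It concerns safety only. The documents state no remission rate, discontinuation rate or exclusion rate, so every efficacy input below is an assumed range.

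**Who is lost.** Three rules have to be read together.

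1. SAP section 8 excludes a patient only if there is no calculable score at any time after the start.
2. SAP section 12 sets the final assessment as "At the final assessment: the data measured at the end during the period from the start date of Humira treatment + 1 day", with the window closing at day +196. It does not require that treatment is ongoing. One score in that window keeps the patient in.
3. Protocol section 6 has the investigator follow a discontinued patient to the end of the 24 weeks. Neither that section nor section 8 schedules a DAS28 at or after discontinuation.

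Stopping early does not in itself remove a patient. Stopping and never being scored does.

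**Effect of leaving out recorded failures.** Let d be the number of never-scored patients who stopped for lack of effect or an adverse event, as a share of scored patients plus these failures. If the rate that counts them as failures is r, the table shows r / (1 − d). With r = 50%:

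| d (assumed) | Calculation | Rate shown | Relative inflation, 1/(1 − d) − 1 |
|---|---|---|---|
| 3% | 0.50 / 0.97 | 51.5% | 3.1% |
| 5% | 0.50 / 0.95 | 52.6% | 5.3% |
| 10% | 0.50 / 0.90 | 55.6% | 11.1% |

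Inflation reaches 10% of the rate at d = 1 − 1/1.1 = 9.1%.

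**Starting from the rate shown.** Let p be the rate shown, e the share of eligible-disease safety-set patients excluded for want of a score, and f the fraction of those excluded who are recorded failures. The supplementary rate is p(1 − e) / [(1 − e) + fe], and d = fe / [(1 − e) + fe]. If all excluded patients are counted, the rate lies between p(1 − e), all failures, and p(1 − e) + e, all successes. With p = 50%:

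| e (assumed) | f = 0.5 | All failures | All successes |
|---|---|---|---|
| 5% | 48.7% | 47.5% | 52.5% |
| 10% | 47.4% | 45.0% | 55.0% |
| 20% | 44.4% | 40.0% | 60.0% |

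The two routes agree. At e = 10% and f = 0.5, d = 0.05 / 0.95 = 5.3%, and 0.50 × (1 − 0.053) = 47.4%.

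**Direction.** Counting recorded failures can only lower the rate or leave it unchanged. The rate shown overstates the rate in all eligible treated patients only if those excluded would have had a rate below p. The documents do not settle that.

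**The case against.** A reader might infer that the rates are inflated, that the bias always favours the drug, or that everyone who stops early is dropped. The documents support none of these.

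- The window from day +1 to day +196 and the follow-up of discontinued patients mean that d may be small. Table 4.2 even lists efficacy at discontinuation, so the SAP expects some early stoppers to have been scored.
- DAS28-4/ESR needs four components. One unmeasured ESR or VAS at each visit can exclude a responder.
- Remission is itself a listed reason for discontinuation. Such patients are also dropped if unscored, and that works in the opposite direction.
- Inside the set, SAP section 9.3 says "the number of patients with “unknown” or “unspecified” data should be included in denominators", which can lower a rate.
- Stopping for an adverse event does not show lack of effect on disease activity. Counting it as ineffective is a choice of composite outcome.
- At an assumed 100 scored patients and a rate of 50%, the 95% half-width is 1.96 × √(0.25/100) = 9.8 points. The shifts of 1.5, 2.6 and 5.6 points are all smaller.
- The exclusions are disclosed: numbers and reasons in Figure 1.1, patients not assessable in Figure 1.2, and individual patients in Tables 4.1 and 4.2.

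The first five stand, and they limit both the wording and the remedy. The sixth is correct, but a confidence interval covers sampling error and not selection, and the documents do not bound d. The last helps only in part. The exclusion category says only that no score was available, so the aggregate tables cannot separate a patient who stopped for lack of effect from one whose ESR was never taken. Table 4.2 holds the discontinuation reason beside the efficacy-set flag, but only as a patient listing.

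**Conclusion.** The concern holds as a risk. A patient recorded as stopping for subtherapeutic response and never scored drops out of every remission rate, every EULAR efficacy rate and every efficacy factor test, and no planned line brings that patient back. The rates may therefore be inflated.

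The size depends on d, which the documents do not give. On a supplementary rate of 50% it is about 1.5 points at d = 3% and 5.6 points at d = 10%, and nothing in the plan suggests that d is as high as 10%. The net direction across all exclusions is open. The effect on the factor tests cannot be quantified from the documents. These figures assume that the recorded reasons are correct and that adverse-event stops are counted as failures by convention.

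**What to change.** Keep the main analysis. For the final-assessment rates in Tables 3.1, 3.5.1, 3.5.2 and 3.5.3, add the following for safety-set patients with an eligible disease. Table 3.1 names no time point at present and should state that one.

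1. A supplementary line that counts as non-remission or ineffective the discontinued patients whose recorded reasons include subtherapeutic response and who have no DAS28-4/ESR after the start.
2. A second line that also counts those with an adverse event as the reason, labelled as a composite-outcome convention.
3. A tabulation of the reason for discontinuation among patients excluded for want of a DAS28-4/ESR, with not discontinued as a category.
4. Bounds with all of these excluded patients counted as failures, and then all as successes.

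Item 3 shows how many excluded patients are recorded failures and how many stopped for remission. Item 4 treats both directions evenly. If there are no never-scored failures, the supplementary and main rates coincide.

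The cost is SAP wording, one short table and a few extra lines, all from data already collected. The supplementary rates may be slightly less favourable.

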## 9. General agreements concerning analysis

### 9.1. Handling of missing data

Missing data will not be complemented, etc. during analysis. However, input data need to be complemented for some items. For the input data requiring complement, the complement methods are defined in the definition of each item in Chapter 10 and subsequent chapters.

### 9.2. Handling incomplete dates

Missing dates should be treated as “unspecified”. Dates including unknown date, month or year, or dates that cannot be true according to the calendar should be handled as “unknown” without exception.

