**2. Target number of patients**

Target sample size: 100 patients

Immediately after the approval of JIA as an indication for treatment with Humira, all patients who receive Humira for the treatment of JIA affecting multiple joints will be registered, and the data for the first 100 patients will be tabulated and analyzed, and the results reported to the regulatory authority. Registration of patients will be continued until the authority concludes its final evaluation.

<Rationale>

Considering the number of patients for whom registration is considered feasible, we will analyze data for 100 patients to detect ADRs with an incidence of 3% at a probability of 95%.

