## 2. Definition of terms and abbreviations

The terms and abbreviations used in this statistical analysis plan are defined as follows.

Terms and abbreviations	Definition
Adverse events	An adverse event refers to any unfavorable and unintended sign (including an abnormal laboratory finding), symptom or disease associated with the use of a drug, whether or not considered related to the drug.
Adverse events during the safety analysis period	Adverse events that occurred during the period up to the start date of Humira treatment + 196 days.
Adverse events outside the safety analysis period	Adverse events that occurred prior to the start date of Humira treatment or after the start date of Humira treatment + 196 days.
Adverse reactions	Of adverse events, events for which causal relationship with Humira cannot be ruled out are defined as adverse reactions.
Adverse reactions during the safety analysis period	Of adverse events during safety analysis period, events for which a causal relationship with Humira cannot be ruled out are defined as adverse reactions during safety analysis period.
Adverse reactions outside the safety analysis period	Of adverse events outside safety analysis period, events for which a causal relationship with Humira cannot be ruled out are defined as adverse reactions outside the safety analysis period.
Basic statistics	Basic statistics include sample size, mean value, standard deviation, minimum value, median value, maximum value, first quartile and third quartile.
MedDRA/J	Medical Dictionary for Regulatory Activities/Japanese edition
SOC	MedDRA/J System Organ Class
PT	MedDRA/J Preferred Term
CDAI	Clinical Disease Activity Index
CRP	C-Reactive Protein
DAS	Disease Activity Score
DMARDs	Disease Modifying Antirheumatic Drugs
EULAR	European League Against Rheumatism
ESR	Erythrocyte Sedimentation Rate
JIA	Juvenile idiopathic arthritis
MTX	Methotrexate
NSAIDs	Non-Steroidal Anti-Inflammatory Drugs
SDAI	Simplified Disease Activity Index
VAS	Visual Analog Scale

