## 10. Data derivation and calculation methods

### 10.1. General

Name of data	Derivation and calculation methods
Age	Use the age shown in the CRF.
Number of investigating facilities	Aggregate the data for each facility code (DCF code).
Number of patients surveyed	Number of patients included in the safety analysis set.
Start date of Humira treatment	Of the start dates of treatment provided in “2. Status of Humira treatment”, the earliest date will be the start date of Humira treatment in each patient. (See “External file for provision of analysis”)
End date of Humira treatment	The latest date sorted by the end dates of treatment provided in “2. Status of Humira treatment” will be the end date of Humira treatment in each patient. (See “External file for provision of analysis”) In the case of ongoing patients, the date on which the final dosing was completed, which is provided in the CRF, will be the end date of Humira treatment. However, in patients whose end date of Humira treatment is “ongoing” or where the end date of Humira treatment calculated as above exceeds the start date of Humira treatment + 168 days, the end date of Humira treatment should be the start date of Humira treatment + 168 days.
Days to the date on which the last dosing of Humira was completed	End date of Humira treatment - Start date of Humira treatment + 1
Treatment status (total number of doses, total dose)	
 
• Total number of doses
 
 
(1) Data on “start date of treatment” and “number of doses” in “2. Status of Humira treatment” should be sorted in the order they are written.
 
(2) Dosing intervals should be calculated for each data on treatment status.
 
The intervals should be 14 days if “biweekly” is checked. If not, the intervals should be obtained from “External file for provision of analysis”.
 
(3) The number of doses should be calculated for each data on treatment status.
 
Number of doses = (end date of treatment [after complementation] - start date of treatment [after complementation])/dosing intervals (days)
 
*The end date of treatment in the last record should be the end date of Humira treatment.
 
(4) If the result of (3) is “>0” (greater than 0) and “<1” (smaller than

Name of data	Derivation and calculation methods

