	
1), it should be 1.
 
If “>=1” (1 or greater), the number should be rounded down to the nearest integer.
 
(5) The total number of doses should be the sum of (4) for each patient.
 
 
• Total dose
 
 
(1) If the dose of Humira is “other”, it should be obtained from “External file for provision of analysis”.
 
(2) Doses should be calculated for each data on treatment status.
 
Dose = number of doses x dose
 
(3) The total dose should be the sum of (2) for each patient.
 
 
• Mean dose
 
 
Mean dose = total dose / total number of doses

Discontinued patients	When the end date of Humira treatment is less than 24 weeks (168 days) after the start date of Humira treatment, the patient should be handled as a discontinued patient.
Reason for discontinuation	In the case of discontinued patients, data should be derived from “Reason for discontinuation” under “3. Discontinuation of treatment” of the CRF or “External file for provision of analysis”. If any data have not been provided, it should be handled as “unknown/unspecified”. “Onset of an adverse event” should apply only when “Onset of an adverse event” is selected and an adverse event during the safety analysis period has occurred.
Date of discontinuation of treatment	In the case of discontinued patients, the end date of Humira treatment should be the date of discontinuation. Where the start date of Humira treatment + 168 days > the end date of Humira treatment, the end date of Humira treatment should be the date of discontinuation.
Patients switched to other biological products	Patients falling under discontinued patients, for whom “Switching to another drug” is selected for “Treatment status after discontinuation” under “3. Discontinuation of treatment” of the CRF and whose “Drug name” falls under codes of biological products listed in “Drug code list 20171012.xlsx”.
Reason for switching	In the case of patients switched to other biological products, data should be derived from “Reason for discontinuation” under “3. Discontinuation of treatment” of the CRF or “External file for provision of analysis”. If any data have not been provided, it should be handled as “unknown/unspecified”. “Onset of an adverse event” should apply only when “Onset of an adverse event” is selected and an adverse event during the safety analysis period has occurred.

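### The SAP treats every partial date as unknown and has no rule placing such adverse events in the safety window; read literally, they fall out of the windowed safety tables

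*SAP*

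**What the plan says.** Four parts of the SAP bear on this.

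- **Incomplete dates (9.2).** "Dates including unknown date, month or year, or dates that cannot be true according to the calendar should be handled as “unknown” without exception". A wholly missing date is labelled unspecified.
- **Missing data (9.1).** "Missing data will not be complemented, etc. during analysis". The exception is for items that need it, for which "the complement methods are defined in the definition of each item in Chapter 10 and subsequent chapters".
- **The safety window (2).** Events during the safety analysis period are "Adverse events that occurred during the period up to the start date of Humira treatment + 196 days". Events outside it are "Adverse events that occurred prior to the start date of Humira treatment or after the start date of Humira treatment + 196 days".
- **Reason for discontinuation and for switching (10.1).** Onset of an adverse event counts as the reason only when that option "is selected and an adverse event during the safety analysis period has occurred".

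Protocol section 2 justifies 100 patients, with feasibility in mind, as enough "to detect ADRs with an incidence of 3% at a probability of 95" percent.

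**The concern.** The survey exists to find unknown reactions and to estimate how often reactions occur. Onset date decides whether a reaction is counted at all, because almost every safety table is limited to the start-to-+196-day window. If a date with a known month and year is reduced to unknown, information that would often settle the matter is thrown away. The patient remains in the denominator, so any loss pushes the reported rate one way only.

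This also runs against the SAP's handling of other event attributes. Under 10.2, any causality other than not related counts as related, and repeated episodes of one PT take the serious and the related value. Onset date has no such cautious default.

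**Working it through.** **1. Is there a completion rule for onset dates?** The exception in 9.1 points to Chapter 10 onwards.
- 10.1 refers to complemented dates only for Humira treatment (the dose-count formula).
- 10.2 covers event terms, seriousness, causality, outcome, onset timing and the during/after-treatment split. It says nothing on partial onset dates.
- Chapter 11 lists seven dated onset intervals with no unknown level, although most of its other factors have one.
- Chapter 12 sets windows for efficacy assessments only.

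So the 9.2 rule applies to onset dates unmodified.

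**2. Where does such an event fall?** Being inside the window requires an occurrence up to start + 196 days. Being outside requires an occurrence before the start or after start + 196 days. An onset handled as unknown can be shown to satisfy neither.

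**3. An example.** Take a patient who starts Humira on some day in January 2013, with a reaction recorded as May 2013, day unknown.
- The latest possible start is 31 January, before 1 May.
- The earliest possible close of the window is 1 January + 196 days = 16 July, after 31 May.
- Every day in May is therefore inside the window, whatever the missing day.
- The 28-day onset layer is not settled. With a 1 January start as Day 1, May runs from Day 121 to Day 151, across the layers for Days 113 to 140 and 141 to 168.

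Window membership is certain here; only the layer is unknown. Rule 9.2 treats both as unknown.

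**4. Which outputs are affected on the literal reading?**

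| Output | Consequence |
|---|---|
| Tables 2.1 to 2.15 and 2.16.1 | Limited to in-window events, so the event is absent |
| Table 2.16.2 | Combines only inside and outside events, so a serious event in neither class is absent |
| Table 4.4 (Appended Form 3), item (20) | *Yes* needs an in-window reaction; *unknown* is kept for unknown event status or an unevaluable patient; the remainder are *no*. A patient whose only reaction is partly dated could be shown as *no* |
| Tables 1.1, 1.2, 2.5.2, 3.2.1 | Adverse event as the reason for stopping or switching is lost only if the patient has no other dated in-window event |
| Table 6.1 and listing 4.2 | Event still appears: 6.1 states no window, and 4.2 lists events for all patients with fixed CRFs |

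**5. Size.** Inputs: n = 100 and incidence 3% (Protocol section 2). Let f be the share of patients with the reaction who are not counted because of an incomplete onset date. The documents do not give f, so the values below are assumptions.

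The plan's own figure first: 1 − (1 − 0.03)^100 = 1 − 0.97^100 = 95.2%, which agrees with the stated 95%.

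With loss f, the countable rate is 0.03 × (1 − f) and the detection probability is 1 − [1 − 0.03 × (1 − f)]^100.

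| f (assumed) | Countable rate | Detection probability |
|---|---|---|
| 0% | 3.00% | 95.2% |
| 5% | 2.85% | 94.5% |
| 10% | 2.70% | 93.5% |
| 20% | 2.40% | 91.2% |

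For a 3% reaction the expected number of patients is 100 × 0.03 = 3. If exactly three occur, losing one moves the reported incidence from 3% to 2%.

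**The case against.** The strongest reply is that no sentence in the SAP tells the programmer to drop these events. Section 9.2 assigns a label, 9.3 keeps unknown values in denominators, and SAP 2 speaks of when an event occurred rather than of how fully its date was recorded. The SAP also refers the construction of the adverse event data to a separate dataset definition document that is not among the papers reviewed, and an allocation rule could sit there. This stands in part: exclusion is the literal consequence of the text, not an explicit instruction, and the behaviour of the programs is not known. However, the SAP cites that document for aggregation, seriousness, causality and outcome, not in the rows on onset timing or on the during/after-treatment split. A rule placed only there would also sit badly with 9.1 and with the absolute wording of 9.2.

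Second, Protocol section 6 provides safeguards: re-query of forms where needed, visits every one or two weeks, and 24-hour notification of serious events. These should make partial dates less common, above all for serious reactions. They cannot recover every date, and 9.2 itself presupposes that some remain incomplete.

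Third, episodes of the same PT in one patient are counted once, so a second, fully dated in-window episode keeps the patient in the count. This narrows the loss without removing it.

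A reader might go further and infer any of the following, none of which the documents support:
- *That the event disappears from all output.* Table 6.1 and listing 4.2 still carry it, although neither restores the reaction count in Appended Forms 2, 3 or 10.
- *That every patient withdrawn for a partly dated reaction loses that reason.* Any other dated in-window event preserves it.
- *That the sample-size justification fails.* An assumed 2% loss gives 94.9%, which still rounds to 95%. The 100 was also set with feasibility in mind, and registration continues beyond it.

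**Conclusion.** The concern holds in a limited form. The SAP has no rule for placing a partly dated adverse event in or out of the safety window, and its stated rule discards month and year information that can settle the question. Followed as written, the event belongs to neither class and is left out of the windowed tables. For a patient with no other reaction, Appended Form 3 could state that there was none.

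The direction is certain under that reading: reaction counts can only fall. The size is not known. The detection figures rest on an assumed share of incomplete dates and on all of those reactions being lost; at 5% to 10% the drop from 95.2% is 0.7 to 1.7 percentage points. The practical weight lies less there than in the chance that one unexpected or serious reaction is missing from a regulatory form in a survey of about 100 patients. It is worth correcting in the SAP, whatever the dataset specification may say.

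**What to change.** - In 9.2 and 10.2, make an exception for adverse event onset. An event with an incomplete or missing onset date counts as in-window unless the known date parts place it wholly before the start date or wholly after start + 196 days.
- Apply the same rule to the adverse-event reason for stopping or switching (Tables 1.1, 1.2, 2.5.2 and 3.2.1) and to Appended Form 3 item (20).
- Add an onset-date-unknown column to Tables 2.14 and 2.15, with the safety analysis set as its denominator, because the existing columns use the number of patients on treatment in each period.
- Footnote the number of such events in the other windowed tables.
- If the dataset definition document already holds a rule, bring it into the SAP and reconcile it with 9.2.

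The cost is one SAP rule and a programming step; no new data are needed. The downside is that a few events truly outside the window may be counted. That should be uncommon, since the CRF covers a 24-week (168-day) observation period and the window runs to +196 days, and the error would be in the cautious direction for safety.
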